5.1 PRIMARY ENDPOINT

The primary endpoint in Phase II is the time-weighted change from baseline in viral shedding over 8 days in site-collected nasopharyngeal (NP) swabs by Quantitative Reverse Transcription Polymerase chain reaction (RT-qPCR), defined as a change from baseline in log10 viral load. Time-weighted average change in log₁₀ viral load from baseline is defined as:

$$\frac{\sum_{i=a}^{b-1} \{0.5 * (Y_i + Y_{i+1}) * (t_{i+1} - t_i)\}}{(t_b - t_a)}$$

- Where
 - *a* = baseline assessment at Day 1
 - b = last assessment at or prior to the threshold day (Day 8 for the primary endpoint)
 - Y_i = change from baseline in \log_{10} viral load at visit i (and where $Y_a=0$)
 - t = time at the specified time point (the actual study day)

The normalisation by the denominator assures comparability of the values if t_b is different between patients.

5.2 SECONDARY ENDPOINTS

5.2.1 Key secondary endpoint(s)

This section is not applicable, as no key secondary endpoints have been specified in the protocol.

[figure not shown]
5.2.2 Secondary endpoints

5.2.2.1 Time-weighted change from baseline in viral shedding over 29 days in site collected NP swabs by RT-qPCR

Time-weighted change from baseline in viral shedding over 29 days in site-collected NP swabs by RT-qPCR is defined as a change from baseline in log_{10} viral load. Time-weighted average change in log_{10} viral load from baseline is defined as described in Section 5.1, but using all measurements through Day 29 (b=Day29).

5.2.2.2 Loss of detection of SARS-CoV-2 RNA by site-collected NP swabs at Day 4, 8, 15, 22 and 29

Loss of detection of SARS-CoV-2 RNA will be evaluated by site-collected NP swabs at Day 4, 8, 15, 22 and 29. Detection of SARS-CoV-2 RNA will be considered as lost at a specific timepoint if the quantitative viral load assessment at this timepoint is below the LOD. Refer to Section 6.7 for the definition of time windows for the different assessment times.

 TSAP for BI Trial No: 1487-0001
 Page 10 of 25

 Proprietary confidential information © 2021 Boehringer Ingelheim International GmbH or one or more of its affiliated companies

Boehringer Ingelheim TSAP for BI Trial No: 1487-0001

Proprietary confidential information © 2021 Boehringer Ingelheim International GmbH or one or more of its affiliated companies

5.4.3 Liver function tests

A listing of all liver function tests will be provided for all subjects who meet one of the following criteria at any time:

- ALT and/or AST ≥3xULN and elevation of total bilirubin ≥2xULN measured in the same blood sample, or in later samples drawn within 30 days after the ALT and/or AST increase
- ALT and/or AST $\geq 10xULN$

5.4.4 Marked changes in vital signs

A marked increase is defined as:

- Systolic Blood Pressure >150 mmHg and increase \geq 25 mmHg above baseline
- Diastolic Blood Pressure >90 mmHg and increase \geq 10 mmHg above baseline
- Pulse Rate >100 bpm and increase \geq 10 bpm above baseline

A marked decrease is defined as:

- Systolic Blood Pressure <100 mmHg and decrease >10 mmHg below baseline
- Diastolic Blood Pressure <60 mmHg and decrease >10 mmHg below baseline
- Pulse Rate <60 bpm and decrease >10 bpm below baseline

6. GENERAL ANALYSIS DEFINITIONS

6.1 **TREATMENTS**

For the definition of treatment administered during the trial, see Section 4 of CTP.

Note: the last day of each of the periods is excluded from the respective period. It defines the first day of the subsequent period.

- Screening: From informed consent to randomisation
- Post-randomisation (optional^[a]): From randomisation to trial drug intake in treatment period
- Treatment period: From date and time of trial drug intake to date of trial drug intake plus one day
- Residual effect period: From the date of trial drug intake plus one day to 90 days plus one day after trial drug intake
- Post-study^[a]: From 90 days plus one day after trial drug intake

[a] This period is optional insofar as it does not necessarily exist for all subjects.

6.2 IMPORTANT PROTOCOL DEVIATIONS

Handling of iPDs in analysis is included in the DV domain specifications and stored within the TMF in EDMS.

No per protocol set analysis will be performed for this study. The proportion of subjects with iPDs will be presented for completeness purposes and to demonstrate the adherence to the CTP.

6.3 SUBJECT SETS ANALYSED

- Screened set (SCS): This subject set includes all subjects having signed informed consent
- Randomised set (RS): This subject set includes all randomised subjects, whether treated or not. This would correspond to the intention-to-treat set (ITT).
- Treated set (TS): This subject set includes all subjects who received any amount of study drug.
- Modified Intention-To-Treat set (mITT): This subject set includes all randomised subjects that received any amount of study drug and who have at least a measurable baseline value (above LLOQ) and a second measurement in the first week (up to 7 days after drug intake) of SARS-CoV-2 RNA by site collected NP swab.

Boehringer Ingelheim TSAP for BI Trial No: 1487-0001

Proprietary confidential information © 2021 Boehringer Ingelheim International GmbH or one or more of its affiliated companies

Please see Table 6.3: 1 for a general overview which patient set will be used for which type of analyses.

Table 6.3: 1	Subject sets	analysed

		Subje	ct set	
Type of analysis	SCS	RS	TS	mITT
Primary endpoint				Х
Secondary endpoints			Х	Х
Safety data, ADA & treatment exposure			Х	
Demographic/baseline characteristics			Х	
Disposition	Х	Х		

Note that the number of subjects with available data for an endpoint may differ. For details, see Section 6.6 "Handling of missing data".

6.5 **POOLING OF CENTRES**

This section is not applicable because centre/country is not included in the statistical model.

6.6 HANDLING OF MISSING DATA AND OUTLIERS

In general, missing data will not be imputed. Missing or incomplete AE dates will be imputed according to BI standards ($\underline{2}$).

6.7 BASELINE, TIME WINDOWS AND CALCULATED VISITS

As a general rule, the last assessment / measurement observed prior to start of trial medication will be assigned to baseline. Note that for some trial procedures (e.g., body weight, vital signs, laboratory tests) this may be the value measured on the same day trial medication was started. In these cases it will be assumed that the measurements were taken prior to the intake of any study medication (if the measurement time was not captured). If no further data available, this can also be the last screening assessment. For viral load related data it is paramount that the sample is taken prior to drug administration, and for these procedures time of sampling will be taken into consideration and compared to the time of drug intake.

Visit windowing will be performed as described in Table 6.7: 1, in order to assign data to the relevant study visit based on the actual day of the assessment. For some endpoints, data will be analysed using the re-calculated visits in the statistical tables. However, in the listings, all visits performed will be displayed (even if outside time-window), along with the re-calculated visit.

Time w	vindow	of actual day ^[1]		Allocated t	0	
Start	(S_n)	End (included)	Length of	Visit	Visit name	Planned day
day		(E _n) day	the time-	number		of the visit
			window	(n)		(V_n)
			[days]			
-4		-2	3	1	Screening	-2
-1		-1	1	2	Baseline	-1
3		5	3	4	Day 4	4
7		9	3	5	Day 8	8
10		17	8	7	Day 15	15
18		24	7	8	Day 22	22
25		33	9	9	Day 29	29
34		105	72	EOS	Day 91	91

Table 6.7: 1	Time windowing rules for site collected viral load related data
--------------	---

^[1] First trial drug intake date is taken into account as a reference to calculate time windows

If after windowing of visits at baseline, two or more values fall within the same baseline interval, then the last value prior to first drug intake will be taken into account. If after windowing of post-baseline visits, two visits fall in the same interval, then the measurement closest to the planned visit will be taken into account. In case two measurements are equidistant from the planned visit, then the last one will be picked.

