- 5 The procedures do not need to be be repeated/performed when V1 and V2 are performed on the same day.
- 6 SARS-CoV-2 laboratory confirmation (antigen or nucleic acid) as a pre-requisite before or at screening (collection within 72 hrs of treatment). The test can be completed via local lab or rapid Point-of-Care device. Result confirmation must be documented and filed in patient records.
- 7 After the individual patient's end of the trial the investigator should report only any cancers of new histology and exacerbations of existing cancer, trial treatment related SAEs and trial treatment related AESIs of which the investigator may become aware of and only via the BI SAE form, please see Section 5.2.6.2.2.
- 8 For remote visits, 11-point WHO Clinical Progression Scale (Section 5.1.2) must be collected by home healthcare nurse or site staff.
- 9 Vital signs measurement shall include BP measurement, body temperature, respiratory rate, pulse rate and resting peripheral oxygen saturation. At screening only respiratory rate, pulse rate and resting peripheral oxygen saturation should be taken to confirm eligibility. Confirmation of PaO2/FiO2 ratio <300 only required in case arterial blood sample was previously taken. At Visit 2, measurements of vital signs should be taken pre-dose, at end of the infusion and 2 hours post study drug administration and precede blood sampling (see Section 5.2.2).

- 10 Complete Physical exam at Visit 1. Complete physical exam includes at a minimum general appearance, neck, lungs, cardiovascular system, abdomen, extremities, and skin. Symptom directed exam at all clinic visits after screening.
- 11 At Visit 2 Site staff will provide a thermometer and pulse oximeter to the participant as well as present and review the study diary. Participants will complete the diary with site staff prior to administration of study drug. On subsequent days with a clinic or remote visit, patients will be reminded to record their temperature, oxygen saturation, and complete all entries every day (preferably the same time every day). Participants will be reminded to bring their diary with them to the next clinic visit. Clinic visit day entry may also be completed at the clinic.

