5.2.2 Vital signs

Vital signs will be evaluated at the time points specified in the flowchart, prior to blood sampling. This includes systolic and diastolic blood pressure, body temperature, respiratory rate, pulse rate (electronically or by palpation count for 1 minute) and resting peripheral oxygen saturation. Measurements must be taken while patient is in a seated position after 5 minutes of rest. The results must be included in the source documents available at the site.

At screening to confirm eligibility only respiratory rate, pulse rate (electronically or by palpation count for 1 minute) and resting peripheral oxygen saturation should be taken. Confirmation of PaO_2/FiO_2 ratio <300 only required in case arterial blood sample was previously taken.

At dosing visit (Day 1), vital signs will be assessed pre-dose, at the end of the infusion and 2h (+/-5 min) after the infusion.

The results must be included in the source documents available at the site.

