6.2.2 Treatment Period(s)

The patient is randomised (Day 1; Visit 2) not later than 3 days after information consent upon confirmation of the eligibility criteria via IRT. Study medication dispensing and administration can occur on the same day (Day 1).

For the schedule of assessments and procedures during the treatment period refer to the Flowchart.

For Dosing and Treatment schedule please refer to Section 4.1.

The below procedures should be completed in the following order prior to trial drug administration. Those listed as optional do not need to be repeated when Visit 1 and Visit 2 are performed on the same day.

- Review of eligibility criteria (optional)
- SARS-Cov-2 symptoms review (optional)
- 11-point WHO Clinical progression scale (optional)
- Medical History (optional)
- Physical examination (optional)
- Vital signs
- Safety blood and urine samples collection
- Serum pregnancy test (see below for details on pregnancy testing)
- Blood samples for inflammatory and coagulation markers
- •
- NP swabs will be collected by site staff (If Visit 2 occurs on the same day as Visit 1 and the sample collected for screening was NP or nasal, the Visit 2 NP sample should preferably be taken from the other nostril). Care must be taken to ensure one (1) sample is taken at screening for eligibility and the second sample is taken as part of V2 procedures.
- •
- Dispensing of study diary
- IRT call (Phase II only: weight needed in IRT for weight-based dosing)

The patient will be monitored for possible infusion reactions and inhalation related reactions (bronchospasm) at the site for approximately 2 hours following study drug administration.

Vital signs will be assessed pre-dose, at end of infusion, and at approximately 2 hours after study drug administration. See Section 5.2.2.

Symptom targeted physical examination will be performed on day of treatment (if V1 and V2 are performed on separate days). See Section 5.2.1

Blood sampling shall be done prior to study drug administration. Patients do not have to be fasted for the blood sampling for the safety laboratory.

Pregnancy test for women of childbearing potential only. Negative urine pregnancy test must be confirmed prior to study drug administration. Serum test required at Visit 2. In case remote visits

are planned during the follow-up period, clinical site may provide subjects with at-home urine pregnancy test kits (may be sponsor-provided).

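### SAP 6.7 allows an untimed Day 1 vital sign to count as pre-dose baseline, although two of the three planned Day 1 readings are post-dose (minor; vital signs are only listed)

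*SAP*

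**What the plan says.** SAP 6.7 gives the general rule that "the last assessment / measurement observed prior to start of trial medication will be assigned to baseline". It adds that "for some trial procedures (e.g., body weight, vital signs, laboratory tests) this may be the value measured on the same day" as the start of medication, and that in such cases "it will be assumed that the measurements were taken prior to the intake of any study medication (if the measurement time was not captured". Viral load is handled more strictly: "for these procedures time of sampling will be taken into consideration and compared to the time of drug intake".

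The protocol describes the Day 1 vital-sign schedule in three places. Section 5.2.2: "vital signs will be assessed pre-dose, at the end of the infusion and 2h" after the infusion. Flow chart footnote 9: "measurements of vital signs should be taken pre-dose, at end of the infusion and 2 hours post study drug administration". Section 6.2.2: "Vital signs will be assessed pre-dose, at end of infusion, and at approximately 2 hours after study drug administration".

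SAP 5.4.4 defines marked changes in systolic pressure, diastolic pressure and pulse rate, each with an absolute limit and a change from baseline. One example is "Systolic Blood Pressure <100 mmHg and decrease >10 mmHg below baseline". SAP 7.8.3 plans a listing of vital signs and no summary tables. Protocol 7.2.6 says that vital signs are to be judged against what was found before treatment began.

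**The concern.** An assumption that untimed dosing-day values precede the dose is safe only for procedures never scheduled after the dose on that day. Vital signs are named among the examples but have two scheduled post-dose readings. SAP 6.7 does not tell the programmer to use the planned timepoint (pre-dose, end of infusion, 2 hours) when the clock time is absent. Read literally, it lets a post-dose reading stand as baseline.

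The readings in question are those taken around the infusion. Protocol Table 1.4.2:1 names hypersensitivity as the anticipated adverse effect, and section 5.2.6.1.4 lists hypotension and tachycardia among the symptoms of cytokine release. If a change in pressure or pulse after dosing is absorbed into baseline, the SAP 5.4.4 flag for that change is lost, and later values are compared with the wrong reference.

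**Working it through.** The plan states no figure on this point. The check sets the rule against the schedule and then applies the SAP 5.4.4 limits.

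**Step 1: schedule.** Planned Day 1 readings: 1 pre-dose + 2 post-dose = 3. Share post-dose = 2/3 = 67%.

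**Step 2: the other procedures named in SAP 6.7.** Flow chart footnote 16 and Protocol 6.2.2 place the Visit 2 blood samples before study drug. Footnote 18 requires weight at randomisation to set the Phase II dose. For these two an untimed Day 1 value is pre-dose if the protocol was followed. Of the three examples, only vital signs have scheduled post-dose readings on Day 1.

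**Step 3: literal application.** If all three readings are untimed, the assumption makes all three eligible as pre-dose. The SAP does not say which to use. Joining the assumption to the general rule (last before medication) points to the 2-hour reading, provided a label or the record order shows which came last. The windows in SAP Table 6.7:1 are for viral load and do not settle it.

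**Step 4: effect on the flags.** The rules in SAP 5.4.4 are:
- marked increase: value > U and value − baseline ≥ d
- marked decrease: value < L and baseline − value > 10
- systolic: U = 150, d = 25, L = 100; diastolic: U = 90, d = 10, L = 60; pulse: U = 100, d = 10, L = 60

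The readings below are assumed for illustration and are not trial data.

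| Parameter | Pre-dose / end of infusion / 2 h | Changes from pre-dose baseline | Flags |
|---|---|---|---|
| Systolic | 130 / 160 / 158 | +30, +28 | 2 increases |
| Systolic | 118 / 92 / 95 | −26, −23 | 2 decreases |
| Diastolic | 75 / 55 / 57 | −20, −18 | 2 decreases |
| Pulse | 82 / 112 / 108 | +30, +26 | 2 increases |

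Total with the pre-dose baseline: 4 × 2 = 8 flags.

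With the 2-hour value as baseline, the end-of-infusion and 2-hour readings no longer count as post-baseline, so there are 0 flags. Even if the end-of-infusion value were still compared, the changes would be 160 − 158 = +2, 92 − 95 = −3, 55 − 57 = −2 and 112 − 108 = +4. None reaches its margin.

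If the end-of-infusion value became baseline instead, the 2-hour changes would be −2, +3, +2 and −4, again 0 flags. The loss therefore does not depend on which post-dose reading is picked.

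**Step 5: the opposite error.** Take pulse 66 / 96 / 92 on Day 1 and 58 at a later visit. From the pre-dose value the fall is 66 − 58 = 8, which is not more than 10, so there is no flag. From the 2-hour value it is 92 − 58 = 34, with 58 < 60, which gives a false marked decrease.

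**The case against.** The strongest reply is that the trigger may never occur. The assumption is a fallback for uncaptured times. Protocol 5.2.2 sets a window of ±5 minutes for the 2-hour reading, which is hard to verify without a time, and Protocol 4.3 requires the dosing time in the eCRF. The eCRF is not among the documents. This stands: the number of untimed readings is unknown and may be zero.

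A second reply is that only a timepoint label or record order could identify the 2-hour value among untimed readings, and a label would also show it to be post-dose. A sensible programmer would then choose the pre-dose reading. This weakens the mechanism but does not remove it, because SAP 6.7 does not give that instruction and its wording points the other way.

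Third, little in the planned output depends on the vital-sign baseline. Vital signs are listed, and the SAP does not say how the 5.4.4 flags will be shown. A fall would still be visible in the raw values. SAP 7.8.1 lists infusion and inhalation reactions from dedicated eCRF pages, and Protocol 5.2.6.1.1 has clinically relevant vital-sign changes recorded as adverse events. This stands and limits the consequence.

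A reader might also infer that the SAP checks timing for viral load alone. It does not go that far: vital signs with a recorded time still fall under the general pre-medication rule. Viral load differs in having an explicit comparison of sampling and dosing times.

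**Conclusion.** The point holds as a conditional defect of minor priority. For untimed Day 1 vital signs, SAP 6.7 as written permits a post-dose baseline, which contradicts Protocol 7.2.6 and can hide or create marked-change flags. This is more than missing detail, since the stated rule names a procedure to which it does not fit.

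The size lies between no patients and the 5 randomised (SAP section 4), depending on how many have untimed readings. Only the marked-change classification and any change from baseline in vital signs are exposed. The raw listing and the efficacy results are not.

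Two stronger readings are tempting. One is that the SAP makes the 2-hour value the baseline. The SAP does not say this; it is an inference from joining two sentences, and it applies only without clock times. The other is that infusion reactions would go undetected. The documents do not support that either, because reactions are reported and listed independently of the programmed baseline.

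The conclusion assumes that the rule is followed literally and that no unpublished programming specification overrides it.

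**What to change.** Amend SAP 6.7, or record the clarification in the report, as follows:
- The vital-sign baseline is the reading planned as pre-dose on Day 1, otherwise the last screening value.
- Readings planned for end of infusion or 2 hours are post-baseline even when untimed.
- The assumption of pre-dose timing is limited to procedures scheduled only before dosing on Day 1, such as body weight and laboratory samples.

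One detail needs stating. Protocol 5.2.2 plans only respiratory rate, pulse rate and oxygen saturation at screening. The screening fallback therefore works for pulse but has no planned value for blood pressure. Where no pre-dose pressure and no screening pressure exist, baseline should be missing and the flag reported as not evaluable.

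The cost is one sentence and one derivation line, with no effect on other analyses. The final SAP (19 October 2021) already postdates unblinding (7 July 2021), so the clarification should be dated. It depends only on planned timepoints, not on treatment arm. With at most 5 patients, their Day 1 listings can also be checked by eye.

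### SAP Table 6.7:1 puts the viral-load baseline window on Day -1 and has no row for Day 1, the day of the pre-dose baseline swab

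*SAP*

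**What the plan says.** Two rules for baseline stand side by side in SAP 6.7.

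- **General rule.** With limited exceptions, "the last assessment / measurement observed prior to start of trial medication will be assigned to baseline". For viral load the section adds that sampling time is compared with the time of drug intake.
- **Table 6.7:1.** This table applies to site-collected viral-load data. The baseline row, whose leading minus sign falls outside the quote, reads "1 -1 1 2 Baseline -1": start Day -1, end Day -1, length one day, Visit 2, planned day -1. The footnote states the reference date: "First trial drug intake date is taken into account as a reference to calculate time windows". A tie-break for baseline begins "If after windowing of visits at baseline, two or more values fall within the same baseline interval" and then takes the last value before first intake.

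The later rows that matter here are "10 17 8 7 Day 15 15", "18 24 7 8 Day 22 22" and "25 33 9 9 Day 29 29" (start, end, length, visit number, visit name, planned day).

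SAP 5.1 starts the time-weighted endpoint at the "baseline assessment at Day 1". In the protocol, Section 6.1 counts visits from Day 1, the Visit 2 dosing date. Flow Chart footnote 13 has the Day 1 swab taken before dosing. SAP 5.2.2.2 and 7.5.2.2 use the windows for loss of detection at Days 4, 8, 15, 22 and 29.

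**The concern.** Baseline feeds every change-from-baseline value. It also decides who has a measurable baseline, which is a condition for the mITT set (SAP 6.3) and for both secondary analyses (SAP 7.5.2). A windowing table that omits the day on which the baseline swab is taken leaves the programmer to decide whether table or text governs. The Day -1 row also matches no scheduled sample, because the Flow Chart's staff-collected nasopharyngeal swabs begin at Visit 2.

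A lesser question is where the post-baseline boundaries fall. If an on-time swab is labelled with the next visit, it can lose out to that visit's own swab, and its own time point is then empty in the by-visit table.

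**Working it through.** **1. The table's own figures.** Length = end - start + 1.

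| Row | Start to end | Computed | Stated |
|---|---|---|---|
| Screening | -4 to -2 | 3 | 3 |
| Baseline | -1 to -1 | 1 | 1 |
| Day 4 | 3 to 5 | 3 | 3 |
| Day 8 | 7 to 9 | 3 | 3 |
| Day 15 | 10 to 17 | 8 | 8 |
| Day 22 | 18 to 24 | 7 | 7 |
| Day 29 | 25 to 33 | 9 | 9 |
| EOS | 34 to 105 | 72 | 72 |

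All eight reproduce, so the table is internally consistent as printed. Going through Days -4 to 105, the days in no row are 0, 1, 2 and 6.

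**2. Could a different day count explain Day -1?** The post-dose planned days (4, 8, 15, 22, 29) are the protocol's days with dosing as Day 1. If dosing were counted as Day 0 instead, the pre-dose swab would fall on Day 0, which is also in no row. Neither count rescues the baseline row.

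**3. Post-baseline boundaries.** The protocol visit windows, read from a Flow Chart table that extracted badly, are ±1 day for Visits 4 and 5, ±2 for Visit 7 and ±4 for Visits 8 and 9. This gives Days 3-5, 7-9, 13-17, 18-26 and 25-33. The midpoints between planned swab days are (4+8)/2 = 6, (8+15)/2 = 11.5, (15+22)/2 = 18.5 and (22+29)/2 = 25.5.

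| Day | Table row | Distance to earlier / later planned day | Protocol window |
|---|---|---|---|
| 6 | none | 2 / 2 | none |
| 10 | Day 15 | 2 / 5 | none |
| 11 | Day 15 | 3 / 4 | none |
| 18 | Day 22 | 3 / 4 | Visit 8 |
| 25 | Day 29 | 3 / 4 | Visits 8 and 9 |
| 26 | Day 29 | 4 / 3 | Visits 8 and 9 |

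Day 2 is also in no row and in none of these swab-visit windows.

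**4. What happens to an on-time Visit 8 swab on Day 25 or 26.** Both days lie in 18-26, so 2 of the 9 permitted days are affected. When two swabs fall in one window, SAP 6.7 keeps the one closer to the planned day and, if equidistant, the later one.

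- Visit 8 on Day 25 is |25 - 29| = 4 days away. A later Visit 9 swab within Days 26-33 is at most 4 days away, so it wins outright or on the tie. The Visit 8 swab is dropped.
- Visit 8 on Day 26 is 3 days away. Visit 9 on Days 27-32 is at most 3 days away and wins. Visit 9 on Day 33 is 4 days away, so the Visit 8 swab is used for Day 29 and the real Visit 9 swab is dropped.

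In each case Day 22 has no value. SAP Section 7 computes percentages over all subjects in the set, including those with missing values. The patient therefore stays in the denominator under the missing category. If the lost swab was below the limit of detection, the Day 22 proportion is understated by one patient.

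**The case against.** The strongest reply is that SAP Section 5 sends the reader to Section 6.7 for baseline definitions, and that section opens with the pre-drug rule. The tie-break in the same section also ends by choosing the last value before first intake. On that reading the Day 1 pre-dose swab is the baseline and the table row is a labelling slip. This stands as to consequence. A reader might infer that a literal run leaves every patient without a baseline and empties the mITT set. That would need the table to override the general rule, and nothing in the SAP says it does. The reply does not remove the contradiction itself.

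On the later windows, the SAP states no nearest-visit rule for boundaries; closeness only settles two values in one window. Days 25-33 are exactly Visit 9 ±4, and Day 18 lies inside Visit 8 ±4. It would therefore be too strong to call those rows wrong. Because the protocol windows for Visits 8 and 9 overlap on Days 25-26, any split by day alone must relabel some on-time swabs. Days 6 and 10-11 can be reached only by off-window or early-discontinuation swabs, and the listings show every visit performed. All of this stands, and it limits the second point to a minor one.

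**Conclusion.** The baseline row is wrong as written. It conflicts with the protocol's Day 1 pre-dose swab, with SAP 5.1 and with the last-value-before-drug rule in the same section. The post-baseline allocation is a secondary defect: two gaps (Days 2 and 6), two days (10-11) sent to the farther visit and outside that visit's protocol window, and two on-time Visit 8 days (25-26) that can lose their swab.

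The reach is limited. SAP 5.1 builds the time-weighted endpoints on actual study day, and SAP 7.5.2.1 uses all measurements to Day 29, so the post-baseline windows affect only the by-visit loss-of-detection proportions. SAP Section 4 reports five randomised patients and no model-based analysis.

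A reader might infer that one lost swab shifts an arm's percentage by 50 to 100 points. The documents do not give the number of patients per arm, so that range is not supported. One patient is worth 100/n points: 100, 50 or 33 for an arm of one, two or three.

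The conclusion on the later windows assumes that the ±1, ±2 and ±4 day windows were assigned to the right visits when read from the Flow Chart.

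**What to change.** 1. Change the baseline row of Table 6.7:1 to Visit 2, Day 1, pre-dose: the last site-collected swab before drug intake, judged by sampling time. Say that the general rule governs if table and text differ.
2. For loss of detection, keep the scheduled visit label for any swab taken within its own protocol visit window. Use the nearest planned post-dose visit only for off-window or early-discontinuation swabs. This sends Day 2 to Day 4 and Days 10-11 to Day 8, and it keeps an on-time Visit 8 swab on Day 25 or 26 at Day 22. Day 6 is equidistant from Days 4 and 8, so name a tie rule for it.

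A pure nearest-visit split (12-18, 19-25, 26-33) is not a cure. Visit 8 on Day 26 would still go to Day 29, Visit 8 on Day 18 would go to Day 15, and Visit 9 on Day 25 would go to Day 22. That makes three relabelled on-time visit-days against two under the present table.

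The cost is one changed row and a short allocation rule, with no new data. SAP Section 8 dates unblinding to 7 July 2021 and the SAP history table dates version 1 to 19 October 2021, so the change should be recorded as a post-unblinding correction.
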